**Table 1 - Day Range for Each Defined Visit/Time for PK and ADA**

Week	Target day a	PK	ADA
W0	1	Day $\leq$ 1	Day $\leq$ 1
D3	3	2 $\leq$ Day $<$ 4	
D5	5	4 $\leq$ Day $<$ 7	
D8	8	7 $\leq$ Day $<$ 10	
D12	12	10 $\leq$ Day $<$ 14	
W2	15	14 $\leq$ Day $<$ 22	
W4	29	22 $\leq$ Day $<$ 43	
W8	57	43 $\leq$ Day $<$ 71	
W12	85	71 $\leq$ Day $<$ 127	2 $\leq$ Day $<$ 127
W24	169	127 $\leq$ Day $<$ 253	127 $\leq$ Day $<$ 253
W48	337	253 $\leq$ Day $<$ 421	253 $\leq$ Day $<$ 421
W72	505	421 $\leq$ Day $<$ 589	421 $\leq$ Day $<$ 589
W96	673	589 $\leq$ Day $<$ 757	589 $\leq$ Day $<$ 757
W120	840	757 $\leq$ Day $<$ 967	757 $\leq$ Day $<$ 967
W156	1092	Day b $\geq$ 967	Day b $\geq$ 967
EOT+2	n.a.	Day c $\geq$ 2	n.a.
Follow-up	n.a.	Day d $\geq$ 2	Day d $\geq$ 2

Week	Target day a	PK	ADA

a Based on days relative to the reference day (ie, the date of first dose of sarilumab).
 
b Excluding the measurements at the end of study follow-up visit (ie, per protocol, 6 weeks after end of treatment visit) and at V88 for PK.
 
c Only applicable to patients who d/c the study during the core treatment phase or not going to enter the extension phase - includes only the measurement(s) at V88 (ie, per protocol, 2 weeks after end of treatment visit).
 
d Includes only the measurement(s) at the end of study follow-up visit V28 (ie, per protocol, 6 weeks after end of treatment visit).
			

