Day	D 113 (±1 or 3)	D 141 (±1 or 3)	D 169 (±1 or 3)	D 225 (±1 or 3)	D 281 (±1 or 3)	D 337 (±1 or 3)	D 421 (±1 or 3)	D 505 (±1 or 3)	D 589 (±1 or 3)	D 673 (±1 or 3)	D757 (±1 or 3)	D 841 (±1 or 3)	D 925 (±1 or 3)	D 1009 (±1 or 3)	Wk 156/EOT	EOS: WK162/EOT+6 Wks
Week	Wk 16	Wk 20	Wk 24	Wk 32	Wk 40	Wk 48	Wk 60	Wk 72	Wk 84	Wk 96	Wk 108	Wk 120	Wk 132	Wk 144		
ANA/anti-dsDNA antibody ^l			X			X		X		X					X ^l	
Local urine pregnancy test for females who are menstruating ^m	X	X	X	X	X	X	X	X	X	X	X	X	X	X	X	
Pharmacokinetics and ADA																
Serum sarilumab ⁿ			X			X		X		X		X			X	X
Antibodies to sarilumab ⁿ			X			X		X		X		X			X	X

Abbreviations: ADA = anti-drug antibody, AE = adverse event, ALP = alkaline phosphatase, ALT = alanine aminotransferase, ANA = antinuclear antibodies, ANC = absolute neutrophil counts, AST = aspartate aminotransferase, BP = blood pressure, DNA = deoxyribonucleic acid, D = day, EOT = End-of-Treatment, EOS = End-of-Study, ESR = erythrocyte sedimentation rate, hs-CRP = high sensitivity C-reactive protein, IMP = investigational medicinal product, IVRS = Interactive Voice Response System, JADAS = Juvenile Arthritis Disease Activity Score, JIA ACR = Juvenile Idiopathic Arthritis American College of Rheumatology, PK = pharmacokinetics, PPD = Purified Protein Derivative, SAE = serious adverse event, TB = Tuberculosis, V = visit, Wk/Wks = week, yrs = years.

- Visit 27 (Week 156) is the study planned End-of-Treatment (EOT) visit. If patients discontinue the study treatment prematurely, EOT will occur 1 week after the last IMP injection for Dose Regimen 3 Cohort and 2 weeks after the last IMP injection for Dose Regimen 1 and 2 Cohorts.
- Visit 28 (Week 162) is the study planned End-of-Study (EOS) visit. If patients discontinue study treatment prematurely, these patients will be asked to return for the End-of-Study (EOS) assessment 6 weeks after the EOT visit (EOT+6 weeks). This EOS visit will be applicable to all the patients in both core treatment phase and extension phase.
- Home diary for IMP administration to be completed for IMP administered at home.
- Complete physical examinations will be performed at Visit 15 (week 24), Visit 18 (Week 48), Visit 20 (Week 72), Visit 22 (Week 96), Visit 24 (Week 120), Week 26 (Week 144), and Visit 27 (Week 156) including skin, nasal cavities, eyes, ears, respiratory, cardiovascular, gastrointestinal, neurological, lymphatic, and musculoskeletal systems.

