Local urine pregnancy test for females who are menstruating ^o			X		X						X			
Pharmacokinetics and ADA														
Serum sarilumab ^p			X						X				X	X
Antibodies to sarilumab ^p			X						X				X	X

Abbreviations: ADA = anti-drug antibody, AE = adverse event, ALP = alkaline phosphatase, ALT = alanine aminotransferase, ANA = antinuclear antibodies, ANC = absolute neutrophil counts, AST = aspartate aminotransferase, BP = blood pressure, DNA = deoxyribonucleic acid, D = day, EOT = End-of-Treatment, EOS = End-of-Study, ESR = erythrocyte sedimentation rate, hs-CRP = high sensitivity C-reactive protein, IMP = investigational medicinal product, IVRS = Interactive Voice Response System, JADAS = Juvenile Arthritis Disease Activity Score, JIA ACR = Juvenile Idiopathic Arthritis American College of Rheumatology, PK = pharmacokinetics, PPD = Purified Protein Derivative, SAE = serious adverse event, TB = Tuberculosis, V = visit, Wk/Wks = week, yrs = years.

- a Visits 13, 14, 16, and 17 are not applicable for patients in the third portion.
- b Visit 16.1 is only applicable for patients in the third portion.
- c Visit 27 (Week 96 for third portion) is the study planned End-of-Treatment (EOT) visit. If patients discontinue the study treatment prematurely, EOT will occur 2 weeks after the last IMP injection.
- d Visit 28 (Week 102 for third portion) is the study planned End-of-Study (EOS) visit. If patients discontinue study treatment prematurely, these patients will be asked to return for the EOT assessment 2 weeks after the last IMP injection and for the EOS assessment 6 weeks after the EOT visit (EOT+6 weeks). The EOT and EOS visits will be applicable to all the patients prematurely discontinued in both core treatment phase and extension phase.
- e Home diary for IMP administration to be completed for IMP administered at home.
- f Complete physical examinations will be performed at Visit 15 (week 24), Visit 18 (Week 48), Visit 20 (Week 72), and Visit 27 (EOT), including skin, nasal cavities, eyes, ears, respiratory, cardiovascular, gastrointestinal, neurological, lymphatic, and musculoskeletal systems.

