- g Investigational medicinal product (IMP) to be administered once every other week (q2w). Patients should be monitored for at least 30 minutes after IMP administration for any signs or symptoms of a hypersensitivity reaction. The last IMP injection will occur at Week 94; then patients will have EOT assessment at the Visit 27 (Week 96 for third portion). There will be no IMP injection at the Visit 27.

- h* Height will be measured using stadiometer at sites during the study.
- i* Juvenile Idiopathic Arthritis American College of Rheumatology (JIA ACR) core set includes: global assessment of the severity of disease by the physician, global assessment of overall well-being by the patient or parent, number of joints with active arthritis (defined as swelling within the joint not due to deformity OR limitation of motion and with either pain, tenderness, or both), number of joints with limitation of motion, Childhood Health Assessment Questionnaire (CHAQ), and hs-CRP (2, 3, 4). If a patient discontinues prematurely before Week 48, hs-CRP must be performed by the central laboratory at EOT.
- j* Juvenile Arthritis Disease Activity Score scoring is explained in [Section 9.4.2](#).
- k* Hematology (blood should be drawn PRIOR TO drug administration): Hemoglobin, hematocrit, red blood cell (RBC) count and morphology (if RBC count is abnormal), white blood cell (WBC) differential (neutrophils, lymphocytes, monocytes, eosinophils, basophils), platelet count, absolute neutrophil count (ANC). If a patient discontinues prematurely before Week 48, the test must be performed by the central laboratory at EOT.
- l* Chemistry (blood should be drawn BEFORE drug administration): ALT, AST, ALP, total bilirubin, conjugated bilirubin, unconjugated bilirubin, and albumin will be tested. Complete chemistry (refer to [Section 9.3.4](#)) should be done at Visit 27 EOT (Week 96 for third portion). If a patient discontinues prematurely before Week 48, the test must be performed by the central laboratory at EOT.
- m* Lipids (blood should be drawn BEFORE drug administration): Triglycerides (TG), total cholesterol, high density lipoprotein (HDL) cholesterol, low density lipoprotein (LDL) cholesterol. Patients are required to fast at least 8 hours before the test. At EOT, the test will be performed only for patient who discontinues prematurely before Week 48 and must be performed by the central laboratory.

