### *ADA incidence and titer*

The following summary will be provided based on the ADA population during the TEAE period:

- Number (%) of ADA-negative patients
- Number (%) of ADA-positive patients
  - Number (%) of patients with neutralizing antibody
  - Number (%) of patients with non-neutralizing antibody
- Number (%) of treatment-emergent ADA-positive patients.
  - The summary statistics (including number, median, Q1, Q3, minimum, and maximum) of the peak post-baseline titer for treatment-emergent ADA-positive patients
- Number (%) of transient treatment-emergent ADA positive patients
  - Number (%) of neutralizing antibody
  - Number (%) of non-neutralizing antibody
- Number (%) of persistent treatment-emergent ADA positive patients
  - Number (%) of neutralizing antibody
  - Number (%) of neutralizing antibody
- Number (%) of treatment-boosted ADA positive patients.
  - Number (%) of patients with neutralizing antibody
  - Number (%) of patients with non-neutralizing antibody

In addition, number (%) of patients with ADA positive or negative response at each visit will be summarized by dose regimen cohort. Persistent and transient ADA responses may be investigated during the extension phase of the trial where multiple ADA assessments are available.

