**Table 2 - Day Range for Each Defined Visit/Time for Lab and Vital Signs**

Week	Target day a			lipids	ANA/Anti-ds DNA antibody	Vital signs (Temperature [pcJIA], HR, BP)	Vital signs (Weight)	Vital signs (Height)
W0	1			Day≤1	Day≤1	Day≤1	Day≤1	Day≤1
D3	3							
D5	5							
D8	8							
D12	12							
W2	15							
W4	29			2≤Day<57		2≤Day<43		
W6	43							
W8	57					43≤Day<71		
W10	71							
W12	85			57≤Day<127	2≤Day<127	71≤Day<99	2≤Day<99	2≤Day<127
W16	113					99≤Day<127	99≤Day<127	
W20	141					127≤Day<155	127≤Day<155	
W24	169			127≤Day<253	127≤Day<253	155≤Day<196	155≤Day<196	127≤Day<253
W32	225					196≤Day<253	196≤Day<253	
W40	253					253≤Day<309	253≤Day<309	
W48	337			253≤Day<421	253≤Day<421	309≤Day<379	309≤Day<379	253≤Day<421
W60	421					379≤Day<463	379≤Day<463	
W72	505			421≤Day<589	421≤Day<589	463≤Day<547	463≤Day<547	421≤Day<589
W84	589					547≤Day<631	547≤Day<631	
W96	673			589≤Day<757	589≤Day<757	631≤Day<715	631≤Day<715	589≤Day<757
W108	756					715≤Day<799	715≤Day<799	
W120	840			757≤Day<925	757≤Day<925	799≤Day<883	799≤Day<883	757≤Day<925
W132	924					883≤Day<966	883≤Day<966	
W144	1008			925≤Day<1051	925≤Day<1051	966≤Day<1051	966≤Day<1051	925≤Day<1051
W156	1092			Day≥1051	Day≥1051	Day b ≥1051	Day b ≥1051	Day≥1051
Follow-up	n.a.			n.a.	n.a.	Day c ≥2	Day c ≥2	n.a.

a Based on days relative to the date of first dose of sarilumab.  
b Excluding the measurements at the end of study follow-up visit (ie, per protocol, 6 weeks after end of treatment visit).  
c Includes only the measurement(s) at the end of study follow-up visit V28 (ie, per protocol, 6 weeks after end of treatment visit).

[figure not shown]

Signature Page for VV-CLIN-0272615 v5.0

Approve & eSign

Approve & eSign

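### SAP Appendix B removes End-of-Study values from the W156 rows only, so third-portion vital signs and weight, and early stoppers' vital signs, weight and ADA, can fill ordinary visit rows

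*SAP*

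**What the plan says.** **Exclusion rule.** In SAP Appendix B, Table 1 (PK and ADA), footnote b reads "Excluding the measurements at the end of study follow-up visit (ie, per protocol, 6 weeks after end of treatment visit) and at V88 for PK". Its closing words, "6 weeks after end of treatment visit) and at V88 for PK", carry the exclusion over to Visit 88. It is attached to one row, W156, which starts at Day 967. In Table 2, footnote b reads "Excluding the measurements at the end of study follow-up visit (ie, per protocol, 6 weeks after end of treatment visit". It is attached to the W156 vital-sign and weight cells, which start at Day 1051. No other row in either table excludes Visit 28 (EOS) or Visit 88 (the extra PK visit).

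**Follow-up row.** The Table 1 footnote for this row says "Includes only the measurement(s) at the end of study follow-up visit V28", and Table 2 has the same rule. This limits what the row may hold. It does not say that those values are used nowhere else.

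**Mapping rule.** SAP 2.5.4 assigns laboratory, vital-sign, ADA and PK values to visits by day since first dose. Where one window holds several values from different dates, it takes the scheduled one nearest the target day. It makes no general exception for Visits 28 or 88.

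**Timing.** For the third portion, protocol 1.2.2.3 says "The last IMP injection will occur at Week 94; then patients will have EOT assessment at the Visit 27 (Week 96 for third portion" and "Visit 28 (Week 102 for third portion) is the study planned End-of-Study (EOS) visit". For early stoppers in the other portions, protocol 1.2.2.1 says "EOT will occur 1 week after the last IMP injection for Dose Regimen 3 Cohort and 2 weeks after the last IMP injection" for Regimens 1 and 2; EOS follows six weeks after EOT.

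**Use.** SAP 2.4.8 says "number (%) of patients with ADA positive or negative response at each visit will be summarized by dose regimen cohort". SAP 2.4.5.4 summarizes vital signs by visit and dose regimen cohort.

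**The concern.** Footnote b shows that the sponsor wants post-treatment samples kept out of treatment-week rows. It is written for patients who finish the 144-week extension, whose EOS falls after the W156 window opens. Third-portion patients finish 60 weeks sooner, and early stoppers can have EOS at almost any time. Their EOS values fall in rows with no such footnote.

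A by-visit row labelled with a treatment week could then hold values taken about eight weeks after the last dose, beside values from patients still on drug. The same measurement might also appear under Follow-up. At stake is how the by-visit vital-sign, weight and ADA tables read.

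**Working it through.** **Inputs.** Windows: SAP Appendix B, Tables 1 and 2. Selection rule: SAP 2.5.4. Phase lengths and visit timing: protocol 1.2.2 and 6.3.1. Visit 28 content: protocol 10.1.11 (vital signs, weight, serum sarilumab, ADA). Day = 7 × week + 1.

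**1. Reproduce the plan's EOS weeks.**
- First and second portions: 12 + 144 + 6 = Week 162, Day 1135. This is inside W156 in both tables and is excluded as intended.
- Third portion: 12 + 84 + 6 = Week 102, Day 7 × 102 + 1 = 715. This agrees with the protocol.

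**2. Third-portion completers, vital signs and weight.** The W108 window is 715 ≤ Day < 799. Visit 23 (Week 108) does not apply to this portion (protocol 10.1.9.3), so nothing competes and the EOS value is used. With the ±3-day visit window, Days 715–718 fall in W108. Days 712–714 fall in W96 (631 ≤ Day < 715), where EOT on Day 673 is on target and is chosen. The last dose was at Week 94, so EOS is (102 − 94) × 7 = 56 days later.

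**3. Third-portion completers, PK and ADA.** Day 715 falls in W96 (589 ≤ Day < 757). EOT on Day 673 is exactly on target and is chosen. EOS enters only if the EOT sample is missing.

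**4. Early stoppers, q2w.** EOT = last dose + 2 weeks and EOS = last dose + 8 weeks. Two examples:
- Last dose Week 40: EOT Day 295, EOS Day 337. Day 337 is the W48 target in both tables, so for ADA the EOS sample displaces the EOT sample.
- Last dose Week 30: EOT Day 225, EOS Day 267. EOS is the only ADA sample in the W48 window (253 ≤ Day < 421).

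Running every even last-dose week before the planned last one through the selection rule, with visits on nominal days and core-phase stoppers attending through Week 12:

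| Portion | Possible stopping weeks | EOS in a row without the footnote: PK/ADA; vital signs/weight | EOS is the chosen value: PK/ADA; vital signs/weight |
|---|---|---|---|
| First and second | 77 (Weeks 0–152) | 65; 71 | 37; 58 |
| Third | 47 (Weeks 0–92) | 47; 47 | 29; 38 |

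These are counts of possible stopping weeks, not patients. They use the target days as printed. Table 2 prints Day 253 for W40, although 7 × 40 + 1 = 281. Using 281 adds one week to each vital-sign and weight count: for last dose Week 34, EOS on Day 295 is 14 days from 281, and EOT on Day 253 is 28 days from it.

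**5. Trough summary.** SAP 2.4.4 drops samples taken less than 11 or more than 17 days after the previous dose (q2w), or less than 5 or more than 9 (qw). EOS is at 56 days (q2w) or 7 + 42 = 49 days (qw). Visit 88 is at 28 or 21 days. None qualifies.

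**6. Visit 88.** The latest case is last dose Day 85, EOT Day 99, Visit 88 Day 113. That never reaches Day 967, so naming Visit 88 in footnote b has no effect.

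**7. TEAE period.** It runs to last dose + 60 days (SAP 2.1.4). On nominal timing, EOS at 56 or 49 days is inside it.

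**The case against.** The best reply is that Appendix B defines rows by days since first dose, not by treatment status. Some off-drug values belong in ordinary rows by design: patients who stop in the core phase attend scheduled visits without dosing through Week 12. A programmer could also take the dedicated EOT+2 and Follow-up rows to mean that each measurement is mapped once. The first argument stands, and it means these rows cannot be called strictly on-treatment. The second is a sensible reading, but the text does not require it: if those rows already captured Visits 28 and 88 exclusively, footnote b would be unnecessary. For the same reason, double reporting is possible rather than prescribed.

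A reader might also infer three stronger things that the documents do not support.
- *The primary PK endpoint is contaminated.* The timing filter removes every on-schedule Visit 28 and Visit 88 sample from the by-visit trough summary. What remains open is serum concentration by ADA status (SAP 2.4.4 and 2.4.8), because the text does not make clear whether the filter covers it.
- *Visit 88 values distort treatment rows.* Visit 88 takes sarilumab PK only, and the scheduled core-phase samples lie on or nearer the target days.
- *A fixed 28% of the W108 row is off drug.* That is 28/(28 + 72), a pooled figure with full attendance on Day 715 or later. It is not a dose-cohort row, and vital signs are summarized by dose cohort.

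**Conclusion.** The rule as written is wrong for two groups.
- **Third-portion completers seen on Day 715 or later:** EOS temperature, heart rate, blood pressure and weight become the W108 result.
- **Early stoppers:** EOS vital signs, weight and ADA can be the chosen value in ordinary rows, and may appear again under Follow-up.

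At most about 28 third-portion patients are concerned. Their share of the selected-dose W108 row depends on attendance day and on attrition in all portions, so no single percentage can be given. The number of early stoppers affected cannot be given either, because the documents contain no distribution of stopping times.

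The effect is limited to descriptive by-visit vital-sign and weight summaries, by-visit ADA percentages for early stoppers, and possibly concentrations by ADA status. The trough summary, third-portion completers' PK and ADA when the EOT sample exists, and TEAE and PCSA counts do not change. No hypothesis is tested. This is a minor correction, worth making because the footnote already shows what the sponsor intended. The conclusion rests on a literal reading of Appendix B and on nominal visit timing.

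**What to change.** Apply footnote b to every post-baseline row in Appendix B Tables 1 and 2. Alternatively, add one sentence to SAP 2.5.4: Visit 28 values map only to the Follow-up row and, for consistency, Visit 88 PK values map only to the EOT+2 row. With either change, the stopping-week counts above in which EOS is the chosen value all fall to zero, and W108 holds no third-portion value from an on-schedule visit. The cost is one sentence or a moved footnote, and a visit-number filter in the programs. No new data are needed, the trough summary does not change, and there is no evident downside.

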**Table 2 - Day Range for Each Defined Visit/Time for Lab and Vital Signs**

Week	Target day a			lipids	ANA/Anti-ds DNA antibody	Vital signs (Temperature [pcJIA], HR, BP)	Vital signs (Weight)	Vital signs (Height)
W0	1			Day≤1	Day≤1	Day≤1	Day≤1	Day≤1
D3	3							
D5	5							
D8	8							
D12	12							
W2	15							
W4	29			2≤Day<57		2≤Day<43		
W6	43							
W8	57					43≤Day<71		
W10	71							
W12	85			57≤Day<127	2≤Day<127	71≤Day<99	2≤Day<99	2≤Day<127
W16	113					99≤Day<127	99≤Day<127	
W20	141					127≤Day<155	127≤Day<155	
W24	169			127≤Day<253	127≤Day<253	155≤Day<196	155≤Day<196	127≤Day<253
W32	225					196≤Day<253	196≤Day<253	
W40	253					253≤Day<309	253≤Day<309	
W48	337			253≤Day<421	253≤Day<421	309≤Day<379	309≤Day<379	253≤Day<421
W60	421					379≤Day<463	379≤Day<463	
W72	505			421≤Day<589	421≤Day<589	463≤Day<547	463≤Day<547	421≤Day<589
W84	589					547≤Day<631	547≤Day<631	
W96	673			589≤Day<757	589≤Day<757	631≤Day<715	631≤Day<715	589≤Day<757
W108	756					715≤Day<799	715≤Day<799	
W120	840			757≤Day<925	757≤Day<925	799≤Day<883	799≤Day<883	757≤Day<925
W132	924					883≤Day<966	883≤Day<966	
W144	1008			925≤Day<1051	925≤Day<1051	966≤Day<1051	966≤Day<1051	925≤Day<1051
W156	1092			Day≥1051	Day≥1051	Day b ≥1051	Day b ≥1051	Day≥1051
Follow-up	n.a.			n.a.	n.a.	Day c ≥2	Day c ≥2	n.a.

a Based on days relative to the date of first dose of sarilumab.  
b Excluding the measurements at the end of study follow-up visit (ie, per protocol, 6 weeks after end of treatment visit).  
c Includes only the measurement(s) at the end of study follow-up visit V28 (ie, per protocol, 6 weeks after end of treatment visit).

[figure not shown]

Signature Page for VV-CLIN-0272615 v5.0

Approve & eSign

Approve & eSign

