	Extension phase (up to 84 weeks of sarilumab exposure from V12 for third portion [Portion 3])													Post-treatment follow-up (6 weeks)			
	V13 ^a D 113 (±1 or 3) Wk 16	V14 ^a D 141 (±1 or 3) Wk 20	V15 D 169 (±1 or 3) Wk 24	V16 ^a D 225 (±1 or 3) Wk 32	V16.1 ^b D 253 (±1 or 3) Wk 36	V17 ^a D 281 (±1 or 3) Wk 40	V18 D 337 (±1 or 3) Wk 48	V19 D 421 (±1 or 3) Wk 60	V20 D 505 (±1 or 3) Wk 72	V21 D 589 (±1 or 3) Wk 84	V27/EOT ^c	V28/EOS ^d					
Concomitant medication			X		X		X	X	X				X			X	
Home diary/compliance ^e			X		X		X	X	X				X				
Physical examination ^f			X				X		X				X				
Call IVRS			X		X		X	X	X				X			X	
Tanner stage and menstruation status			X				X	X	X				X			X	
Treatment																	
IMP administration ^g			X		X				X			X	X	X			
IMP dispense			X		X				X			X	X	X			
Vital signs																	
Temperature, heart rate, blood pressure			X		X				X			X	X	X			X
Weight			X		X				X			X	X	X			X
Height (stadiometer) ^h			X						X			X	X	X			X

Visit	Extension phase (up to 84 weeks of sarilumab exposure from V12 for third portion [Portion 3])												Post-treatment follow-up (6 weeks)				
	V13 ^a D 113 (±1 or 3) Wk 16	V14 ^a D 141 (±1 or 3) Wk 20	V15 D 169 (±1 or 3) Wk 24	V16 ^a D 225 (±1 or 3) Wk 32	V16.1 ^b D 253 (±1 or 3) Wk 36	V17 ^a D 281 (±1 or 3) Wk 40	V18 D 337 (±1 or 3) Wk 48	V19 D 421 (±1 or 3) Wk 60	V20 D 505 (±1 or 3) Wk 72	V21 D 589 (±1 or 3) Wk 84	V27/EOT ^c	V28/EOS ^d					
JIA ACR core set ⁱ			X				X		X				X				
JADAS-27 ^j			X				X		X				X				
Safety assessment																	
AE/SAE recording			X		X					X			X				X
Tuberculosis risk assessment			X		X					X			X				X
PPD tuberculin skin test for patients ≤5 years; QuantiFERON-TB test for patients > 5 years										X							
Local tolerability			X							X			X				X
Laboratory testing																	
Hematology ^k			X		X					X			X				X ^k
Chemistry ^l			X		X					X			X				X ^l
Fasting lipids ^m			X							X							X ^m
hs-CRP			X							X			X				X ⁱ

Visit	Extension phase (up to 84 weeks of sarilumab exposure from V12 for third portion [Portion 3])											V27/EOT ^c	Post-treatment follow-up (6 weeks) V28/EOS ^d	
	V13 ^a D 113 (±1 or 3) Wk 16	V14 ^a D 141 (±1 or 3) Wk 20	V15 D 169 (±1 or 3) Wk 24	V16 ^a D 225 (±1 or 3) Wk 32	V16.1 ^b D 253 (±1 or 3) Wk 36	V17 ^a D 281 (±1 or 3) Wk 40	V18 D 337 (±1 or 3) Wk 48	V19 D 421 (±1 or 3) Wk 60	V20 D 505 (±1 or 3) Wk 72	V21 D 589 (±1 or 3) Wk 84				
ESR			X			X			X			X		
ANA/anti-dsDNA antibody ⁿ			X			X			X ⁿ					

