10.1.9.3 Patients enrolled directly under the selected dose regimen in the third portion

For detailed information on the procedures for patients who are recruited directly under the selected dose regimen in the third portion, see the flow chart in [Section 1.2.2.3](#).

10.1.9.3.1 Visit 15 (Week 24), Visit 16.1 (Week 36), Visit 18 (Week 48), Visit 19 (Week 60), Visit 20 (Week 72), Visit 21 (Week 84)

- Record all concomitant medications use with start date and dose in the patient's e-CRF
- Inquire regarding AEs/SAEs
- Check home diary/compliance
- Provide home diary. All patients or their parents or guardians will record information pertaining to injections performed at home (date, time, injection location, and any problems)

- Record vital signs including body temperature, BP, and HR
- Record weight (kg)
- Record patient height at Visit 15 (Week 24), Visit 18 (Week 48), and Visit 20 (Week 72)
- Check Tanner stage and menstruation status at Visit 15 (Week 24), Visit 18 (Week 48), and Visit 20 (Week 72) (see Appendix F)
- Perform a complete physical examination including skin, nasal cavities, eyes, ears respiratory, cardiovascular, gastrointestinal, abdominal, lymphatic, neurological systems, and musculoskeletal systems at Visit 15 (Week 24), Visit 18 (Week 48), and Visit 20 (Week 72)
- Perform the joint count assessments to note JIA disease manifestations (articular and extra-articular) and assess disease activity (ensure JADAS -27 joints are included) at Visit 15 (Week 24), Visit 18 (Week 48), and Visit 20 (Week 72)
- Ask the patient/parent(s)/guardian(s) to complete relevant questionnaires: functional ability determined by CHAQ and (parent or guardian)/patient assessment of overall well-being at Visit 15 (Week 24), Visit 18 (Week 48), and Visit 20 (Week 72). All questionnaires should be documented in the subject's study file. Each VAS score should be copied on the patient's e-CRF
- Complete the physician global assessment of disease activity at Visit 15 (Week 24), Visit 18 (Week 48), and Visit 20 (Week 72)
- Perform a tuberculosis risk assessment. In case of suspicion of tuberculosis, refer the patient to a specialist for a complete examination and additional work-up

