- Perform PPD tuberculin skin test for patients ≤ 5 years or QuantiFERON-TB test for patients > 5 years at Visit 18 (Week 48); QuantiFERON-TB test will be considered in the younger group of patients (≤ 5 years) based on the local PPD availability, local regulation for PPD screening, and the Investigator's judgments
- Collect blood for hematology (see [Section 9.3.4](#)), chemistry including ALT, AST, ALP, total bilirubin, conjugated bilirubin, unconjugated bilirubin, and albumin
- Collect blood for fasting lipids at Visit 15 (Week 24) and Visit 18 (Week 48)
- Collect blood for hs-CRP at Visit 15 (Week 24), Visit 18 (Week 48), and Visit 20 (Week 72)
- Collect blood for ESR at Visit 15 (Week 24), Visit 18 (Week 48), and Visit 20 (Week 72)
- Collect blood for ANA/anti-dsDNA at Visit 15 (Week 24) and Visit 18 (Week 48)
- Collect blood samples for serum sarilumab, antibodies to sarilumab at Visit 15 (Week 24), Visit 18 (Week 48), Visit 20 (Week 72) (see [Section 9.1](#) and the study flow chart [Section 1.2](#))
- Perform urine pregnancy test locally for female patients who have commenced menstruating for each visit

- Call IVRS to register the visit and get the treatment kit number(s) assigned to each patient along with the dose volume to be administered
- Dispense the IMP
- Administer the IMP
 - During the course of the extension phase (starting at Visit 12), the IMP injection dose can be adjusted. Refer [Appendix B](#) for injection volume based on the patient's weight
 - Patients should be monitored for at least 30 minutes after IMP administration for any signs or symptoms of a hypersensitivity reaction
- Check local tolerability (see [Section 9.3.3](#))
- Schedule the appointment for the next visit and request patients to come in a fasting condition at Visit 15 (Week 24), Visit 18 (Week 48)

Visits 13, 14, 16, 17, 22, 23, 24, 25, and 26 are not applicable for patients enrolled in the third portion.

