#### **2.1.4.5 Vital signs variables**

Vital signs include heart rate, systolic and diastolic blood pressure (SBP and DBP), temperature, height, and weight. At each visit where blood pressure is scheduled, two assessments, at least 1 minute apart, will be performed and recorded according to procedures described in the protocol.

The schedule of vital sign assessments can be found in can be found in Section 1.2 Study Flow Charts of the protocols [REDACTED]

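### SAP Appendix B Table 2 has no Week 36 window for third-portion vital signs and weight, and prints the Week 40 target day as 253 instead of 281

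*SAP*

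**What the plan says.** SAP 2.5.4 maps laboratory values, vital signs, ADA and PK to scheduled visits by days from first dose. When several scheduled values fall in one window, it keeps the one nearest the target day. For laboratory tests and vital signs the windows are in Appendix B Table 2, "Day Range for Each Defined Visit/Time for Lab and Vital Signs". In its temperature/heart rate/blood pressure column and its weight column, W32 (target 225) covers Days 196 to 252. The next row, W40 (target printed as 253), covers Days 253 to 308.

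For the visits themselves the SAP defers to the protocol. SAP 2.1.4.5 states: "The schedule of vital sign assessments can be found in" the protocol flow charts. The third-portion flow chart (Protocol 1.2.2.3) gives Visit 16.1 as "D 253 (±1 or 3) Wk 36" and Visit 17 as "D 281 (±1 or 3) Wk 40". Its footnotes add: "Visits 13, 14, 16, and 17 are not applicable for patients in the third portion" and "Visit 16.1 is only applicable for patients in the third portion".

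Protocol 10.1.9.3.1 covers a run of visits that begins "Visit 15 (Week 24), Visit 16.1 (Week 36), Visit 18 (Week 48" and continues to Visit 21. It requires vital signs and weight at all of them. Hematology and "chemistry including ALT, AST, ALP, total bilirubin, conjugated bilirubin, unconjugated bilirubin, and albumin" are collected at the same visits.

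**The concern.** A third-portion patient seen at Week 36 has a protocol visit with no label in the table that assigns labels. Because mapping is by study day, the value goes to whichever neighbouring row its day falls in, and neither of those visits applies to that patient. Day 253 lies on the boundary between the two rows, so a one-day difference in scheduling decides the label.

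The W40 target has a different fault. It sits on the first day of its own window and disagrees with the protocol's Week 40 day. It comes into play when a patient has more than one candidate value in that window.

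What is at stake is the accuracy of the by-visit descriptive tables in SAP 2.4.5.4. No value is lost, but values appear under the wrong week and no Week 36 result would exist.

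**Working it through.** **Inputs.** Target days and windows come from SAP Appendix B Table 2. Visit days come from the flow charts in Protocol 1.2.2.1 and 1.2.2.3. The tolerance is ±3 days for every-other-week dosing (Protocol 6.3.1), and footnote g of 1.2.2.3 gives that interval for the third portion.

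**1. The target column.** With first dose on Day 1, target = 7 × week + 1. Of the 22 weekly rows:
- 16 match exactly, for example W32: 7 × 32 + 1 = 225, and W48: 7 × 48 + 1 = 337.
- Five (W108, W120, W132, W144, W156) are 1 day low.
- W40 is 28 days low: 7 × 40 + 1 = 281, against 253 printed. Day 253 is Week 36: 7 × 36 + 1 = 253.

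**2. The W40 limits.** Most limits in these columns are midpoints between adjacent targets.
- With target 281: (225 + 281)/2 = 253 and (281 + 337)/2 = 309. These are the printed limits.
- With target 253: (225 + 253)/2 = 239 and (253 + 337)/2 = 295. These are not the printed limits.

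The window was therefore built on 281, and the printed 253 is a misprint rather than another day convention.

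**3. Visit 16.1 through the printed windows.**

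| Study day | Label under Table 2 |
|---|---|
| 250, 251, 252 | W32 |
| 253, 254, 255, 256 | W40 |

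That is 3 of 7 days to W32, 4 of 7 to W40 and 0 of 7 to W36. A visit exactly on Day 253 is labelled W40. Its distance is 253 − 225 = 28 days from Week 32 and 281 − 253 = 28 days from Week 40.

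**4. When the wrong target matters.** Suppose a third-portion patient attends Visit 16.1 on Day 253, has a last injection on Day 267 and stops treatment. Footnote c of Protocol 1.2.2.3 puts the End-of-Treatment (EOT) visit two weeks later: 267 + 14 = 281. Protocol 10.1.10 records vital signs and weight there. Both visits fall in Days 253 to 308.
- Target 253: distances 0 and 28, so Visit 16.1 is kept.
- Target 281: distances 28 and 0, so EOT is kept.

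**5. Windows with a W36 row.** Using targets 225, 253, 281 and 337, the midpoints are 239, 267 and 309.

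| Visit | Permitted days | Proposed window | Label |
|---|---|---|---|
| 16 | 222 to 228 | 196≤Day<239 | W32 |
| 16.1 | 250 to 256 | 239≤Day<267 | W36 |
| 17 | 278 to 284 | 267≤Day<309 | W40 |

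Each regular visit maps to its own week. In the step 4 example, Visit 16.1 goes to W36 and EOT to W40, so both are shown.

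**The case against.** Extraction from PDF might be blamed for the missing row, since other columns of Table 2 are incomplete. That does not work for these two columns: the W32 and W40 windows meet at Day 253 and leave no room for a lost row. Nor does the SAP predate the third portion. Its sections 1.1, 3 and 4 describe that portion, its 84-week extension, its interim analysis and its database lock.

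A fair objection is that only the W40 target is an arithmetic error, while the absent W36 row is an omission in window design. That is right. The omission still matters, because the stated mapping rule then produces a wrong label.

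It may also be said that the target is harmless to third-portion patients because Visit 16.1 is their only visit between Days 196 and 308. That overlooks premature EOT visits. The SAP rule that moves a discontinuation visit to the next planned visit covers efficacy only.

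The strongest objection is size: one label in descriptive tables, in a study with no hypothesis tests. This stands, and it sets the severity.

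Three stronger readings are tempting but unsupported.
- **Hematology and chemistry** are collected at Visit 16.1, but their windows are not visible, so no error can be claimed for them.
- **Dose-switched patients.** A patient who switches at Visit 16 (Day 225) has Visits 103, 104 and 105 on Days 253, 267 and 281, all inside the W40 window. However, post-adjustment data are summarized separately under SAP 2.4.11, which is not visible.
- **Safety signals.** Incidence of potentially clinically significant abnormalities (PCSA) counts all evaluations in the treatment-emergent period and does not use these windows.

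**Conclusion.** Both faults hold as described. Severity is minor.

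- **Missing W36 window:** no permitted Visit 16.1 day can be labelled W36, and either label given is 28 days off for a visit on Day 253. This affects up to about 28 planned third-portion patients, fewer after dropout.
- **W40 target:** printed 28 days early. It can change the value selected for any patient with several candidate values in Days 253 to 308, whether from a premature EOT visit or from unscheduled measurements.

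The effect stays within descriptive by-visit summaries of temperature, heart rate, blood pressure and weight. PCSA incidence, efficacy and primary PK are unaffected.

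The conclusion assumes that Table 2 is applied as printed to all three portions. The selection example also assumes that an EOT measurement counts as scheduled under SAP 2.5.4. If it were treated as unscheduled, Visit 16.1 would be kept under either target.

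**What to change.** In Table 2:

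- Set the W40 target day to 281.
- In the temperature/heart rate/blood pressure and weight columns, add a W36 row with target Day 253 and use W32 196≤Day<239, W36 239≤Day<267 and W40 267≤Day<309. The outer limits, 196 and 309, stay as printed.
- Check the hematology and chemistry columns and add the same rows if they show the same split.

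No study-portion key is needed. A single W36 window over Days 196 to 308 for third-portion patients would be a poorer choice. It would reach 253 − 196 = 57 days from its target, and it could merge a Day 252 visit with a Day 280 EOT visit that now appear separately.

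The cost is one row, one target cell, two adjusted limits per affected column and a small change to the mapping code, with no new data. The new row will hold almost only third-portion patients. Because W32 and W40 become narrower, some unscheduled or EOT values from other patients may be labelled W36.
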